In France, many of them use this type of treatment and more specifically fasciatherapy during the various phases of low back pain (Trudelle 2003), believing that it improves their physiotherapy management of low back pain (Courraud & al 2016). Other studies have also highlighted the effects of the application of fasciatherapy in the management of fibromyalgia pain (Dupuis 2016), the treatment of anxiety (Payrau & al 2017), general discomfort (Angibaud & al 2013) and the body perception Duval & al 2010, Courraud 2007). These findings underscore the multidimensional impact of fasciatherapy and its potential for clinical, functional, and psychosocial benefits in the context of LBP treatment.

Fasciatherapy, like osteopathy from which it derives, is one of the manual therapies that target the fascial system and its various functions. This "patient-centered" therapeutic technique is rooted in a biopsychosocial and humanistic approach to health (Bois 2008). Fasciatherapy focuses on the fascia—defined as a membrane or sheet enveloping and connecting various body structures, such as muscles, joints, viscera, vessels, and nerves (Terminologia Anatomica, code A04.0.00.031, Adstrum et & 2017). This tissue is the subject of numerous scientific investigations and its involvement in various musculoskeletal pathologies such as low back pain is regularly mentioned. The architectural changes (tensions, rigidifications and fascial adhesions) observed by imaging are likely to produce acute and chronic pain. Manual and gestural treatment techniques for the fascial system are therefore among the promising Non-Medicinal Interventions (NMI). Fasciatherapy techniques involve manual and exercice therapy, the aim of which is to restore the contractile, elastic and movement properties of the fascial system in order to bring relief and improve the function and/or quality of life of people suffering from low back pain. These techniques are called 'non-manipulative' because they do not use forced mobilisation of the tissues.

In France, however, fasciatherapy is not included in professional recommendations and is not recognised as a title, specificity or qualification by the Conseil National de l'Ordre des Masseurs-Kinésithérapeutes (CNOMK 2012).

The aim of this study is therefore to highlight the effects of fasciatherapy on low back pain through an assessment of pain, quality of life, functionality and anxiety. It also aims to observe how fasciatherapy could contribute to the management of low back pain in the context of massage and physiotherapy.

This is a randomised cluster study with pain as the primary endpoint, involving 180 participants. The evaluation criteria include pain assessment using the Visual Analogue Scale (VAS), functional assessment using the Dallas Pain Questionnaire, quality of life evaluation with the SF-12 questionnaire, psychological assessment of anxiety using the STAI, and monitoring of medication use based on information provided by patients to the practitioner.

The practical conduct of the study is structured as follows:

- Recruitment of physiotherapists (investigators) by the FasciaFrance association and verification via their Curriculum Vitae of the investigators' inclusion criteria,
- Randomization of investigators into three groups based on the care they will provide: massage-physiotherapy care, combined massage-physiotherapy and fasciatherapy care, and fasciatherapy-only care.,
- Distribution of the investigator's brochure and observation booklet,
- Each investigator recruits their patients and adheres to the protocols outlined in the investigator's guide and observation booklet.
- Submission of anonymized ("coded") data by the investigators to the study sponsor.
- Data entry in the ACCESS database,
- Statistical analysis of the data using STATA software,
- Publication of the results.

CONTENTS

1	Gen	eral information	6	
	1.1	Title of research	6	
	1.2	Coordination and monitoring of the study - promoter	6	
	1.3	Coordinating investigator	6	
	1.4	Co-investigator - scientific collaborator - investigator - statisticians and associate partn	er 6	
	1.5	Study locations	7	
	1.6	Study timetable	7	
2	Stuc	ly rationale and scientific justification	7	
3	Aim	s of the study	9	
	3.1	Main objective	9	
	3.2	Secondary objectives	9	
4	Stuc	ly category	9	
	4.1	Search category	9	
	4.2	Justification for qualification	9	
5	Pop	Population studied / concerned		
	5.1	Inclusion criteria	9	
	5.2	Non-inclusion criteria	9	
	5.3	Procedure for early termination of research	10	
	5.4	Recruitment procedures	10	
6	Des	cription of the study	10	
	6.1	Assessment criteria	10	
	6.1.	Primary endpoint	10	
	6.1.2	2 Secondary evaluation criteria	10	
	6.2	Investigation method used	10	

1.1 Title of research

The benefits of fasciatherapy for the treatment of chronic low back pain in physiotherapy: a randomised cluster study

Short title : Fasciatherapy and chronic low back pain

1.5 Study locations

As this is a multi-centre study, patients will be enrolled in the practices of healthcare professionals (investigators) practising massage physiotherapy and fasciatherapy. Authorisation for research site: not applicable

1.6 Study timetable

CPP submission: 14 December 2020 Study start date: effective start date: 6 May 2021 Recruitment period: 6 May 2021 to 6 June 2023 Patient follow-up period: 3 months maximum Total duration of the study: 28 months Anticipated end of study (last patient visit): 6 September 2023 End of study report: May 2024

2 Study rationale and scientific justification

Low back pain is defined as pain located between the thoracolumbar junction nd the lower gluteal fold. It may be associated with radicular pain which is pain in one or both lower limbs at the level of one or more dermatomes. Common low back pain refers to pain in the lower back that occurs without any specific warning signs (see "red flags"). The term "common" low back pain is preferred to "non-specific" low back pain in everyday practice. Chronic low back pain is defined as low back pain lasting more than 3 months (HAS 2019).

Questionnaires can be used to assess the risk of chronic low back pain. The French National Authority for Health (HAS) recommends the use of the STarT Back screening tool (which offers risk-stratified management) and the short version of the Örebro questionnaire (which predicts absenteeism), both of which have a grade B recommendation (scientific presumption).

According to current knowledge, the causes of common chronic low back pain are multifactorial (Seminowicz & al 2011, Fayt 2010, May and George 2011). Although there are recommendations for physiotherapy for the sub-acute and chronic phases, the treatment protocol is not well defined (HAS 2000, 2005). New therapeutic models centered on neuro-physiology are gradually replacing models

based on biomechanics, and new programmes centered on patient education and a biopsychosocial approach are beginning to emerge (Nijs & al 2011).

Recent research has highlighted the possible involvement of fascia in low back pain (Langevin & al 2011, Willard & al 2012, Schilder & al 2013, Hoheisel & al 2015, Wilke & al 2017) and studies have shown the role of manual fascia therapies in the treatment of low back pain (Tozzi & al 2011, Branchini & al 2016, Harper & al 2015, Gordon & al 2015). To date, there are no studies that have demonstrated the effects of fasciatherapy in the treatment of common low back pain although physiotherapists are increasingly interested in the role of fascia in the management of musculoskeletal pathologies (Kwong and Findley 2014) including low back pain (Viklund & al 2015, Ajimsha & al 2014).

In France, many patients opt for this type of treatment, particularly fasciatherapy, during the different phases of low back pain. (Trudelle 2003), believing that it improves their physiotherapy management of low back pain (Courraud & al 2016). Other studies have also highlighted the effects of the application of fasciatherapy in the management of fibromyalgia pain (Dupuis 2016), the treatment of anxiety (Payrau & al 2017), general discomfort (Angibaud & al 2013) and the perception of the body (Duval & al 2010, Courraud 2007). These studies bear witness to the multidimensional action of fasciatherapy and justify its clinical, functional and psychosocial evaluation in the context of its action on low back pain.

Fasciatherapy, like osteopathy from which it derives, is one of the manual therapies that target the fascial system and its various functions. This "patient-centered" therapeutic technique is rooted in a biopsychosocial and humanistic approach to health (Bois 2008). It essentially targets its action on the fascia, an anatomical entity described as a membrane, sheet or envelope that covers, surrounds and compartmentalises the different parts of the human body (muscles, joints, viscera, vessels, nervous system) while linking them together (Terminologia Anatomica, code A04.0.00.031, Adstrum & al. 2017). This tissue is currently considered to be the anatomical element that maintains the shape and architectural unity of the body, while ensuring interaction between the different parts.

It has been the subject of numerous scientific investigations over the last few decades, and its involvement has been demonstrated in various fields. From a biological perspective, inflammation originates in and is managed by the fascia. In biomechanics, fascia acts as the vector for the transmission of muscular force and the organization of movement. It is also involved in neuro-sensory phenomena such as proprioception, nociception, and interoception.

Its role in various musculoskeletal pathologies such as low back pain is also regularly mentioned. The architectural changes (fascial tensions, rigidifications and adhesions) observed by imaging are likely to produce acute and chronic pain. Manuel or exercice therapytechniques for the fascial system are therefore among the promising Non-Medical Interventions (NMI).

Fasciatherapy techniques involve manual and exercice therapy aimed at restoring the contractile, elastic and movement properties of the fascial system, with a view to providing relief and improving the function and quality of life of people suffering from low back pain. The manual and gestural techniques used are "non-manipulative" (no forced mobilisation of tissues). The practitioner applies manual and/or gestural tension to the fascia with the aim of achieving self-regulation of tension and tightness in the various fascial structures. In the treatment of low back pain, fasciatherapy techniques will be applied specifically to the thoracolumbar fascia and its various connections (lower limbs, lumbar, thoracic and cervical spine, shoulder girdle and abdomen).

In France, however, fasciatherapy is not included in professional recommendations and is not recognised as a title, specificity or qualification by the Conseil National de l'Ordre des Masseurs-Kinésithérapeutes (CNOMK 2012).

3 Aims of the study

3.1 Main objective

To evaluate the specific benefits of 5 fasciatherapy sessions, alone or in combination with physiotherapy, on the pain experienced by patients suffering from chronic low back pain.

3.2 Secondary objectives

- Assessing the benefits of fasciatherapy in the physiotherapy and massage treatment of low back pain
- Demonstrate the beneficial impact of fasciatherapy on the various aspects of chronic low back pain (pain, anxiety, function, quality of life)
- Identify the aspect(s) of low back pain for which fasciatherapy is most effective.

4 Study category

4.1 Search category

RIPH category: category 2

Fasciatherapy: non-manipulative manual and gestural therapy.

4.2 Justification for qualification

The interventional research study involves only minimal risks and constraints with regard to the list set by the decree of 03/05/2017.

5 Population studied / concerned

5.1 Inclusion criteria

Patients will be included:

• At the time of the practitioner's first consultation for this condition, the patient had been diagnosed with chronic low back pain and had no red flags.

The judgement criteria used to confirm the chronic nature of low back pain independently of the presence of pain lasting more than 3 months were :

- the STarT Back Screening Tool (Grade B recommendation by the HAS), which identifies the risk of chronicity in a patient with low back pain,
- the VAS scale, which assesses pain intensity,
- Functional Assessment using the DALLAS Self-Assessment Questionnaire (French version of the DRAD validated by the S.F.R. Spine Section), which assesses the impact of pain on quality of life,
- Patients aged between 30 and 60.
- 5.2 Non-inclusion criteria

Patients should not :

- Present with specific low back pain (systemic rheumatic pathology, compression due to a tumour, neurological pathology of central origin, etc),
- Present with psychiatric pathologies (apart from the usual comorbidities of chronic low back pain),

- Be pregnant or breastfeeding,
 - Be under guardianship or curatorship,
- Be deprived of liberty or under a court protection order
- Be incapable of giving consent
- Being unable to complete questionnaires.

5.3 Procedure for early termination of research

The patient cannot participate simultaneously in another study in order to avoid interactions between studies, the cumulative effect of care and to guarantee the homogeneity of the groups. There is no exclusion period, and patients may participate in another clinical research protocol as soon as their participation in this study has ended.

5.4 Recruitment procedures

Patients are included in the protocol by each practitioner participating in the study, as part of their usual practice. Any patient consulting a practitioner participating in the study for chronic low back pain may be included in the study. The practitioner will ensure that the inclusion and exclusion criteria are respected. At the first appointment, the patient is informed about the study and given an informed consent form. A minimum of 48 hours elapses between the consent form being handed over and the patient's consent being collected.

6 Description of the study

6.1 Assessment criteria

6.1.1 Primary endpoint

The main evaluation criterion will be pain, measured using the VAS (visual analogue evaluation) scale (Moquet 1999) to assess pain levels, before and after each session.

6.1.2 Secondary evaluation criteria

- Functional assessment using the DALLAS Self-Assessment Questionnaire (French version of the DRAD validated by the S.F.R. Spine Section) completed at the start of treatment (1st session) and at the end of treatment (5th session);
- Assessment of Quality of Life using the SF-12 Quality of Life questionnaire (short form) completed at the start of treatment (1st session) and at the end of treatment (5th session);
- Psychological assessment using the STAI Y questionnaire (Spielberg's State-Trait Anxiety Inventory). The STAI YA measuring the state of anxiety is completed at the beginning and end of each session. The STAI YB measuring trait anxiety is completed at the start of treatment (1st session) and at the end of treatment (5th session).
- Any changes in the usual/current use of medication (analgesics and psychotropic drugs) prescribed for low back pain, by collecting information at each session.

6.2 Investigation method used

This is a cluster randomised clinical trial.

The methodology is pragmatic:

- Patients with common chronic low back pain were included, regardless of co-morbidities,
- The comparative intervention is physiotherapy,

- The instructions for implementing the experimental or control intervention are flexible, leaving the practitioner considerable latitude in the application of the intervention,
- The experimental and control intervention is deployed under all clinical conditions, with attention paid only to the dose delivered and to side effects,
- There is no follow-up of patients after the end of the study.

Three groups of low back pain patients will be selected:

- A group receiving only conventional physiotherapy;
- A group receiving both conventional masso-physiotherapy and fasciatherapy treatments;
- A group receiving fasciatherapy treatments only.

All patients will receive 5 sessions over a maximum period of 3 months. The frequency of the sessions will be determined by the practitioner, and the duration of each session may vary from 30 to 45 minutes in order to respect the usual ways of practising masso-physiotherapy and fasciatherapy. The study will be limited to 5 sessions because a previous survey of physiotherapists practising fasciatherapy showed that they carried out an average of 5 fasciatherapy sessions for the treatment of a patient with low back pain. In order to be able to compare the groups, we decided to use this number of sessions. As the number of physiotherapy sessions was defined by each physiotherapist following the physiotherapy assessment, there was a risk of differences in the number of sessions between the groups and between practitioners in the same group. For this reason, we also chose to limit the study to 5 sessions. However, patients will of course be able to continue with the sessions if this proves necessary.

The choice of specific techniques used by the practitioner is left to his or her discretion, whether for physiotherapy (massage, physiotherapy, exercises, etc.) or fasciatherapy (manual therapy, exercise, etc.).

The only additional procedures compared with ordinary care are the secondary assessment questionnaires.

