7.2 Description of procedures performed on individuals (description of each visit)

7.2.1 Physiotherapy group (Group 1)

The masso-physiotherapy procedures recommended by the HAS (2005) and in accordance with the Nomenclature Générale des Actes Professionnels (NGAP) for the treatment of low back pain are as follows:

- physical exercise,
- massage,
- electrotherapy,
- spinal traction,
- adjuvant treatments (balneotherapy, cryotherapy, etc).

The choice of procedures and their combination is left to the discretion of the practitioner according to his initial assessment, the needs and possibilities of the patient and his therapeutic preferences (in accordance with the principles of EBM).

In this study, practitioners are encouraged to keep to the usual session time of between 30 and 45 minutes.

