7.2.3 Fasciatherapy group (Group 3)

Practitioners only carry out fasciatherapy procedures using manual (myofascial, articular, visceral) and/or gestural treatment techniques. The choice of procedures, their order of application and their combination is left to the discretion of the practitioners, depending on their assessment and the patient's clinical progress.

The length of sessions observed (Courraud, 2015) is 30 to 45 minutes. Participating practitioners will be encouraged to respect this time.

The fasciatherapy techniques used in this study are 'non-manipulative' (i.e. no forced manipulation of joints or soft tissues), manual and gestural (no use of instruments or adjuvant products) and aim to restore the mechanical properties of the fascias (sliding, elasticity, mobility) in order to restore their function (continuity, contractility, sensitivity). The maneuvers are performed very slowly (with each stretch lasting about 15 seconds), resulting in a gradual and global stretching of the fascia in the

lumbar region and its distant connections. During this stretching, the practitioner establishes a support point (holding the stretched fascia) to alter the fascial tone. The practitioner evaluates areas of tension and tightness in the lumbar fascia to guide the treatment plan and identify the specific areas to address.

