7.3 Description of the general logistical organisation of the trial

Practitioners will receive an observation booklet by post. Each practitioner will include between 3 and 5 patients in the study.

The promoter is responsible for gathering all the data collected at each phase of the study and at the end of the study. They will compile the data into an Excel file and transmit it to the statistician.

- 7.4 Inclusion criteria for practitioners
 - Qualified physiotherapist,
 - Private practice,
 - Having a mixed practice combining conventional physiotherapy and fasciatherapy which is outside the scope of conventional practice,
 - Having completed at least 105 hours of training in fasciatherapy.

8 Data collected

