8.1.2 Observation booklet and investigator's brochure

Investigator brochure :

- Cover page mentioning "Investigator Brochure"
- Investigator instruction sheet
- General overview of the study
- Investigator memo: "What to do and when for each patient?"
- Filling instructions
- CV and characteristics sheet of the investigator physiotherapist
- Correspondence table
- A copy of the self-administered questionnaires

Observation book :

- Cover page mentioning "Observation Notebook"
- Patient eligibility sheet (inclusion and exclusion criteria)
- Patient dividers and temporal dividers for the investigator's reference
- Patient information form
- Patient consent form in two copies
- Administrative and medico-social patient sheet
- Anonymized evaluation questionnaires and the Visual Analog Scale (VAS) sheet, distributed according to the study protocol

- Patient follow-up sheet (dates, session description, medications, significant events), divided into five sections
- Serious Adverse Event (SAE) reporting sheet

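### Section 6.2 says delivered dose and side effects are watched, but neither is an evaluation criterion and section 9.1 plans no by-arm summary of either

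*Combined protocol and SAP*

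**What the plan says.** Section 6.2 lists the features of a pragmatic design. One is flexible instructions, "leaving the practitioner considerable latitude in the application of the intervention". Another is deployment under all clinical conditions, "with attention paid only to the dose delivered and to side effects". The quantity of treatment is largely fixed: "All patients will receive 5 sessions over a maximum period of 3 months", each of 30 to 45 minutes. The content is not: "The choice of specific techniques used by the practitioner is left to his or her discretion".

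Section 6.2 defines Group 1 as receiving conventional physiotherapy only. Section 7.2.1 lists its procedures (exercise, massage, electrotherapy, traction, adjuvants) and adds: "The choice of procedures and their combination is left to the discretion of the practitioner according to his initial assessment". For Group 3, section 7.2.3 is explicit: "Practitioners only carry out fasciatherapy procedures using manual (myofascial, articular, visceral) and/or gestural treatment techniques". In Group 2 (section 7.2.2) the split of time between the two approaches is left open.

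Section 7.4 requires of every practitioner, whatever the arm: "Having a mixed practice combining conventional physiotherapy and fasciatherapy which is outside the scope of conventional practice". At least 105 hours of fasciatherapy training are also required.

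For recording, section 8.1.2 provides a follow-up sheet for each of the five sessions (dates, session description, medications, significant events) and a "Serious Adverse Event (SAE) reporting sheet".

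**The concern.** The main objective in section 3.1 is the specific benefit of fasciatherapy, so the trial depends on the arms differing in what is delivered. The Group 1 practitioners are trained in fasciatherapy. Their permitted procedures include massage and exercise, and section 2 describes fasciatherapy as manual and exercise therapy. Some carry-over into Group 1 is therefore plausible. Without a by-arm account of delivered content, a small or null difference could mean either no specific effect or a weakened contrast, and the report would give little help in telling them apart.

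For harms, the only dedicated form covers serious events. A non-serious reaction such as dizziness or fatigue (examples assumed here) is noted only if the treating practitioner, who knows the arm, judges it significant. The trial could then say little about whether one approach produces more ordinary reactions than another, although section 6.2 says side effects are watched.

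**Working it through.** The point rests on what the plan contains, not on a stated figure, so the first check is to set the sections side by side.

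| Section | Delivered treatment | Side effects |
|---|---|---|
| 6.1.1, 6.1.2 | Not listed | Not listed; pain, state anxiety and medication are collected at each session |
| 8.1.2 | Dates and session description | Significant events; SAE sheet |
| 9.1.1 | Protocol deviations described; no definition of a technique deviation | None |
| 9.1.2, 9.1.3 | None | Pain and the per-session anxiety score compared by group and session; no adverse event analysis |
| 9.1.4 | None | None |
| 10.3 | Adherence checked at monitoring visits | Not named |

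Both items are partly recorded, neither is a criterion, and no by-arm summary of either is planned.

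**Is fasciatherapy already excluded from Group 1?** Read together, yes. Section 6.2 restricts Group 1 to conventional physiotherapy. Section 7.2.1 ties its procedures to the HAS recommendations and the NGAP. Section 2 says fasciatherapy is outside professional recommendations, and section 7.4 places it outside conventional practice. But section 7.2.1 lacks the explicit restriction found in 7.2.3, and no section says which recorded technique would count as a deviation.

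**Illustration of dilution.** The documents give no crossover rate. Let c be the share of the fasciatherapy effect that reaches Group 1 (assumed). Observed difference = (1 − c) × true difference. Section 9.2 takes 1 to 2 points as clinically relevant.

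- True 1.0: 1.0 × 0.8 = 0.8 at c = 20%; 1.0 × 0.6 = 0.6 at c = 40%.
- True 2.0: 2.0 × 0.8 = 1.6; 2.0 × 0.6 = 1.2, still above 1 point.

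For power, the inputs from section 9.2 are two-sided alpha 1.7%, 60 per group, within-patient correlation 0.5 over 5 sessions and ICC 0.05 to 0.2. Assumed within the stated ranges: difference 1.5, SD 2.5, and 4 patients per practitioner (section 7.3 allows 3 to 5). No dropout is assumed.

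- Repeated-measures factor: (1 + 4 × 0.5)/5 = 0.6.
- Design effect: 1 + 3 × 0.05 = 1.15, or 1 + 3 × 0.2 = 1.6.
- Effective n: 60/1.15 = 52.2, or 60/1.6 = 37.5.
- Standard error: 2.5 × √0.6 × √(2/n) = 0.379, or 0.447.
- Power = Φ(1.5(1 − c)/SE − 2.387).

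| c | ICC 0.05 | ICC 0.2 |
|---|---|---|
| 0 | 0.942 | 0.833 |
| 10% | 0.880 | 0.736 |
| 20% | 0.782 | 0.617 |
| 30% | 0.649 | 0.485 |

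At difference 2 and SD 2.5, power at c = 20% is still 0.967 (ICC 0.05) or 0.883 (ICC 0.2). The effect of carry-over thus depends heavily on inputs the plan leaves as ranges. Section 9.2 makes no stated allowance for it.

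**What a harms table could show.** Power = Φ((|p1 − p2| − 1.96√(2p̄(1 − p̄)/n)) / √((p1(1 − p1) + p2(1 − p2))/n)), with p̄ the mean of p1 and p2, and n = 60 divided by the design effect. The rates are assumed. For 10% against 30% of patients with at least one event, power is 0.789 with no clustering, 0.730 at design effect 1.15 and 0.584 at 1.6. For 10% against 20% it is 0.333, 0.296 and 0.225. Such a table describes with intervals; it is not a powered test.

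**The case against.** Much can be said for the plan, and most of it stands.

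- A reader might infer that ordinary reactions, including a pain flare after a session, go uncompared. The documents do not support that. Pain before and after each session is the primary endpoint, and section 9.1.2 compares groups at each session. A flare that lasts would also raise the next pre-session score. State anxiety is measured at each session too. What is left is non-serious reactions that show in none of these, in research that section 4.2 classes as minimal risk.
- A reader might infer that crossover is invisible to the plan. It is not: session descriptions are kept, section 9.1.1 commits to describing deviations, and section 10.3 has adherence reviewed. What is missing is a definition of a technique deviation and a by-arm summary.
- Dose can fairly be read as quantity, which section 6.2 largely fixes. On that reading, what is unreported is sessions actually received and minutes; technique content is a related but separate matter.
- A reader might take the attention to dose and side effects as the reason for allowing free choice of technique. Section 6.2 lists them as neighbouring features and does not give one as the reason for the other.
- The forms themselves are not in the documents, only their list of contents, so the follow-up sheet may be more structured than its title suggests.

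None of this supplies a uniform question about reactions, a definition of crossover or a table by arm.

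**Conclusion.** The point holds as a reporting and recording gap. The plan names two things it will watch, partly collects both, and commits to summarising neither by arm. The consequence is that a null result would be harder to interpret and that little could be said about non-pain, non-serious reactions.

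It would go too far to call a null result uninterpretable: this is a declared pragmatic comparison, and deviations will be described. It would also go too far to attach a size. The dilution and power figures rest on an assumed c, on proportional dilution and on chosen values within the ranges of section 9.2; no crossover or reaction rate appears in the documents. Nor do they show that section 7.2.1 allows fasciatherapy in Group 1. The text taken together points the other way, but section 7.2.1 does not say so itself. This is a cheap improvement worth making, not a flaw in the primary analysis.

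**What to change.** 1. **Side effects.** Add one fixed question, answered by the patient before sessions 2 to 5, on any new or worsened symptom since the last session (yes/no, what, how long). List adverse events as a secondary criterion in section 6.1.2. In section 9.1, report by arm the patients with at least one event, and SAEs, with intervals that allow for practitioner clustering. The question covers the intervals after sessions 1 to 4, at most 180 × 4 = 720 of 180 × 5 = 900 sessions; reactions after session 5 would still be unsolicited.
2. **Delivered treatment.** Record techniques on a checklist using the protocol's own terms in sections 7.2.1 and 7.2.3, with session minutes. Tabulate delivered content, minutes and sessions received by arm.
3. **Crossover.** Reconcile section 7.2.1 with the definition of Group 1 in section 6.2. If that definition stands as written, count fasciatherapy recorded in Group 1 as a deviation and report it under section 9.1.1.

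An analysis that excludes sessions whose content does not match the arm is not recommended, because it selects after randomisation.

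The cost is a revised session sheet, about a minute more recording per session and two extra tables, with no change to sample size or primary analysis. A limit remains: a checklist completed by the treating practitioner may miss fasciatherapy handling that is ticked as massage.

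The timetable in section 1.6 puts the last visit in September 2023. If collection has ended, code the existing session descriptions, significant events and SAEs, and report them by arm.
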